8.3.3 Enrollment Completion

Investigational sites will be notified to cease enrolling subjects for this study when the enrollment target is reached or at the sponsor's discretion in consultation with FDA. This notification is expected to happen when at least 1,616 subjects have been enrolled.

8.4 Investigator/Site Selection Criteria

The sponsor will consider many factors to ensure selection of sites and investigators that are qualified through their training and experience to properly conduct the study. Diverse sites will be selected with respect to geography and clinical setting (e.g., university, private practice, etc.). The current BSC process for evaluating and selecting clinical sites will be utilized. The evaluation and selection criteria include but are not limited to the following:

- Participation in the S-ICD Clinical Investigation (G090013)
- Sites that have the personnel with knowledge to run a clinical study and enroll subjects according to FDA and good clinical practice guidelines. It is recommended that sites have a dedicated Research Coordinator and exceptions will be evaluated on a case-by-case basis
- Sites that have a Principal Investigator (physician) who has a commitment to conducting research and is in good standing with the FDA

- Sites that have the necessary knowledge and experience to implant CRM products and also have the potential subject volume to meet enrollment expectations
- Site personnel that have a commitment to protocol compliance along with gathering and submitting timely and accurate data using an electronic data entry system
- Sites that will support on-site clinical data monitoring during the study

8.5 Justification for the Study Design

The S-ICD Post Approval Study is designed to assess long term safety and effectiveness outcomes associated with the implantation of the SQ-RX pulse generator and Q-TRAK subcutaneous electrode in a commercial clinical setting. As such, it is designed as a standard of care registry that will compare observed measures of safety and effectiveness at 5 years to performance goals that were derived from the same endpoints observed at shorter time periods (e.g., 1 year) in the S-ICD Clinical Investigation (IDE G090013). The S-ICD Post Approval Study will also provide an active reporting mechanism for close monitoring of device performance during the initial US commercialization, permitting characterization of low-frequency adverse events.

9. SUBJECT ACCOUNTABILITY

9.1 Point of Enrollment

A participant in the S-ICD Clinical Investigation (IDE G090013) who is implanted with the S-ICD System is considered enrolled upon signing the informed consent form (ICF). Subjects who did not participate in the S-ICD Clinical Investigation (IDE G090013) will be considered enrolled after both signing an informed consent and undergoing an implant procedure. A subject who signs an informed consent, but does not undergo an implant procedure does not count toward the enrollment ceiling and has no follow-up requirements.

9.2 Withdrawal

All subjects enrolled in the clinical study (including those withdrawn from the clinical study or lost to follow-up) shall be accounted for and documented. If a subject withdraws from the clinical investigation, the reason(s) shall be reported.

10. STATISTICAL CONSIDERATIONS

[figure not shown]
The S-ICD Post Approval Study is designed to examine the long-term safety and effectiveness of the S-ICD System. The study design includes two co-primary endpoints maintaining a family-wise significance level of 0.05 by defining a hierarchical testing procedure. The safety endpoint will be tested first. If the test is successful then the effectiveness endpoint will be tested at the same significance level. Primary endpoints will be tested prior to testing the secondary endpoints. Individual rates of each adverse event contributing to the primary safety endpoint will be examined including two-sided 95% exact confidence intervals. Other pre-specified observational analyses are defined to further investigate the long-term safety and effectiveness of the S-ICD System.

Subjects from the IDE study who provide informed consent for this study will be followed through 60 months post implant. All subjects enrolled in the S-ICD System Clinical Investigation (IDE G090013) who underwent an implant attempt will contribute to the analyses of the safety and effectiveness endpoints and additional analyses. Data from IDE subjects who do not provide consent for the study or subjects who previously exited the IDE will be censored at the time of IDE study exit in the endpoint analyses, but will not count toward the target enrollment sample size. All non-IDE subjects who undergo an implant procedure for the S-ICD System will be included in the endpoint analyses and will count toward the enrollment ceiling. All analyses may be done separately on IDE study subjects vs de novo implants. The statistical analyses related to this study will be executed by the sponsor and/or business partners working on behalf of the sponsor.

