7.2.9 Annual Follow-up Visit

After implant, scheduled follow-up visits are to be performed annually (± 60 days) from the implant date in order to capture:

- Spontaneous episodes that have not been previously reported;
- Adverse events that have not been previously reported;
- Programming changes that have not been previously reported;
- Product experience reports that have not been previously reported.

For participants in the S-ICD Clinical Investigation (IDE G090013), annual follow-up visit windows are calculated from the original S-ICD System implant date (day 0) and take into account the last follow-up visit conducted in the S-ICD Clinical Investigation (e.g., if the last follow-up conducted in the S-ICD Clinical Investigation (IDE G090013) was the 540 day follow-up visit, then the first S-ICD PAS annual follow-up visit should occur at 720 days post implant).

Aside from the annual follow-up visit, other scheduled and unscheduled visits throughout the year (e.g., standard of care device checks) should not be submitted unless they are associated with a Type I-II clinical event, device episode, suspected device malfunction or device programming change¹⁷, in which case they should be submitted as additional follow-up visits as described in Section 7.2.10, below.

The final annual follow-up visit must occur more than 1800 days after the initial implant procedure. The first standard of care visit within the annual follow-up visit window that occurs after the 1800 day mark should be submitted as an annual follow-up visit; if that is not possible, then the next standard of care visit may be submitted as an additional follow-up visit to allow for timely study completion. **Table 7** lists all the data required at annual follow-up visits.

¹⁷ A programming change refers to any difference between *Initial Device Settings* and *Current Device Settings* under the *Programmable Parameters* section of an S-ICD Summary Report.

Table 7: Annual Follow-Up Visit Data Collection

Data Collection	Retention of Original Source Documentation
Adverse events, if applicable	Investigational Center
Q-TECH Programmer Printouts: - Initial and Final Summary Reports - Captured S-ECG in each sensing vector - Device episodes, if applicable Shocked induced VT/VF episodes (external ECG strips), ¹⁸ if performed Chest x-ray(s) if applicable ¹⁹	Investigational Center; upload copy to Cameron Health/BSC
SD Card Data	Cameron Health/BSC (e.g. via CAMELION)

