7.4 Study Completion

Subjects may be withdrawn from the study for a variety of reasons including:

- Subject withdraws consent for any reason;
- Subject is lost to follow-up despite best efforts to locate the subject;
- The S-ICD System is permanently explanted;
- The subject has been followed >60 months from the original implant date.

Subjects who undergo a permanent explant or who commence, but do not complete, an implant procedure should be contacted, either in person or by telephone, at least 30 days after the permanent explant or implant attempt in order to record any adverse events before being withdrawn from the study. The study completion form documents withdrawal of any subject from the study.

There are no additional follow-up requirements once a subject has been withdrawn from the study. **Table 10** lists all the data that are required for study completion.

Table 10. Study Completion Data Collection

Data Collection	Retention of Original Source Documentation
Adverse events, if applicable	Investigational Center
Q-TECH Programmer Printouts: - Initial and Final Summary Reports - Captured S-ECG in each sensing vector, if sensing vector changed - Device episodes, if applicable Shocked induced VT/VF episodes (external ECG strips), ²⁵ if performed Death letter, if applicable Chest x-ray(s) if applicable ²⁶	Investigational Center; upload copy to Cameron Health/BSC
SD Card Data (if new spontaneous episodes were recorded)	Cameron Health/BSC (e.g. via CAMELION)

²⁵ Induction testing is not required per protocol; upload only if performed. Any time induction testing is performed in the study, external ECG strips are only required for sustained ventricular arrhythmias that result in a shock, either from the S-ICD System or from an external defibrillator.

²⁶ An X-ray is not required per protocol; upload only if a chest x-ray of the S-ICD System was taken to assess the position of the S-ICD System, an S-ICD System-related adverse event, or suspected product issue.

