10.1.2 Primary Safety Endpoint Hypothesis

The primary safety endpoint null and alternative hypotheses are as follows:

Ho: The Type I Complication Free Rate at 60 months (p1) does not exceed the performance goal of 85.0%.

$$Ho: p1 \leq 85.0\%$$

Ha: The Type I Complication Free Rate at 60 months (p1) does exceed the performance goal of 85.0%.

$$Ha: p1 > 85.0\%$$

²⁷ *Permanent loss of device function* refers to: 1) the permanent loss of shock therapy and/or post shock pacing; 2) permanent loss of appropriate sensing in all available sensing configurations (oversensing that results in persistent inappropriate shocks or undersensing that could lead to undetected arrhythmias). Loss of device function includes programming the PG permanently off or temporarily off in advance of an explant/revision.

The null hypothesis will be rejected if the lower one-sided 95% confidence bound²⁸ of the Kaplan-Meier estimate, using the Peto method for standard error, exceeds the performance goal of 85.0%.

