10.3.1 Primary Effectiveness Endpoint Performance Goal

10.3.2 Primary Effectiveness Endpoint Hypothesis

The primary effectiveness endpoint null and alternative hypotheses are as follows:

Ho: Overall Shock Effectiveness in Converting Spontaneous Discrete Episodes of VT/VF through 60 months (p_1) does not exceed the performance goal of 94.0%.

$$Ho: p_1 \leq 94.0\%$$

Ha: Overall Shock Effectiveness in Converting Spontaneous Discrete Episodes of VT/VF through 60 months (p_1) does exceed the performance goal of 94.0%.

[figure not shown]
$$Ha: p_1 > 94.0\%$$

The null hypothesis will be rejected if the lower one-sided 95% exact confidence bound of the estimate exceeds the performance goal of 94.0%.

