10.6.1 Target Sample Size

10.7 Data Analysis

10.7.1 Safety Endpoint Analyses

The primary safety endpoint will be evaluated as the proportion of subjects free from Type I Complication at 60 months based on the Kaplan-Meier method including the one-sided lower 95% confidence interval.³⁰

The secondary safety endpoint will be evaluated as the proportion of subjects free from Electrode Related Complication at 60 months based on the Kaplan-Meier method including the one-sided lower 95% confidence interval.³⁰

The Kaplan-Meier analysis will take into account the time from implant until the occurrence of the complication and data from any subjects who are complication-free will be right censored at the last known follow-up including subjects who exited the study.

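### If any IDE roll-over subject has an interval between leaving the IDE study and consenting to this study, the plan counts it as time at risk with no delayed entry, which biases the 60-month safety rates and survival upward

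*Combined protocol and SAP*

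**What the plan says.** All references are to the combined protocol and SAP.

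- **Who contributes (section 10).** Every IDE subject with an implant attempt enters the safety and effectiveness analyses. "Data from IDE subjects who do not provide consent for the study or subjects who previously exited the IDE will be censored" at the date of IDE exit. Those who consent to the PAS are followed to 60 months after implant.
- **Clock (10.7.1).** "The Kaplan-Meier analysis will take into account the time from implant until the occurrence of the complication". Complication-free subjects are right-censored at last follow-up. Nothing readable mentions late entry to the risk set.
- **Enrollment (9.1, 8.3.1).** An IDE participant enrolls on signing PAS consent. Section 9.1 describes that person as currently implanted, while the inclusion criterion asks only for a previous implant.
- **Explant (7.4).** One listed reason for withdrawal is: "The S-ICD System is permanently explanted".
- **Event typing (11.3).** An event that arose outside enrollment is Type IV, so it cannot be a Type I complication.
- **Collection (7.2.9).** Annual visit windows count from the original implant. Visits capture "Spontaneous episodes that have not been previously reported", and likewise adverse events not yet reported.
- **Tests (10.1.2, 10.3.2).** For safety: "The null hypothesis will be rejected if the lower one-sided 95% confidence bound" (Kaplan-Meier, Peto standard error) exceeds 85.0%. For shock effectiveness, an exact one-sided 95% bound on episodes must exceed 94.0%. Safety is tested first and opens the way to effectiveness (section 10).

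**The concern.** Before IDE exit there is no selection, because all implanted IDE subjects contribute. After PAS consent, observation is ordinary. The difficulty lies only in the stretch between, if there is one. A subject who died in that stretch cannot sign, and one who was permanently explanted does not fit section 9.1. Both are censored at IDE exit and their events are never recorded. A subject who comes through and consents is credited with the whole stretch. This is immortal time, and censoring the non-consenters at IDE exit does not remove it, because the person-time left in the gap belongs only to those selected for having passed through it.

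Section 11.3 may add to this for the primary endpoint. A consenter's own device-caused complication in the gap was outside enrollment and would be Type IV, while the time stays in the denominator. Section 7.2.9 nevertheless collects earlier unreported events, so the two sections point in different directions.

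The error runs one way, toward passing, and it falls on the primary safety test that gates the others.

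**Working it through.** **Plan figures.** The assumptions behind 1,616 are redacted, so it cannot be reproduced and is not in question here. The timeline does reproduce: 18 + 60 = 78 months.

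**Inputs from the documents.** Safety goal 85.0% at 1800 days (10.1.2, 6.1); 1,616 subjects, first enrollment about 4 months after PMA approval, enrollment complete 18 months later (7.1); 330 IDE subjects (Introduction).

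**Assumed, because the documents do not say.** Gaps of 4, 13 and 22 months, taking IDE exit at PMA approval: 4, 4 + 18/2, and 4 + 18. A gap of 6 months is added because the example in 7.2.9 runs from a day-540 IDE visit to a day-720 PAS visit, 180 days apart. Other assumptions are a constant hazard, a roll-over share w of the risk set during the gap of 6% to 18.6%, and a fraction L of gap events that goes uncounted.

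**Large-sample formula.** With T = 1800/365.25 = 4.928 years and h = -ln(S)/T, the estimate becomes S × exp(h × w × g × L), g in years. For S = 0.85, h = 0.0330 per year.

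- 6 months, L = 1, w = 0.06: 0.85 × [exp(0.0330 × 0.06 × 0.5) - 1] = +0.08 points. With w = 0.186: +0.26. With L = 0.5: +0.04 and +0.13.
- 22 months, L = 1, w = 0.186: 0.85 × [exp(0.0330 × 0.186 × 1.833) - 1] = +0.96.
- True rate 95% (h = 0.0104), same worst case: +0.34.
- Electrode-related rate at its 92.5% goal (h = 0.0158), same worst case: +0.50. Section 10.2.1 defines that endpoint by event category and timing, not by type, so the Type IV rule does not on its face apply and L should be lower.

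**Simulation.** True Type I rate 85.0%, 1,616 subjects, 10% attrition per year, IDE exit 12 to 24 months after implant, Peto bound, 1,500 trials per setting. Naive means gap time is counted. False pass means the lower bound exceeds 85%.

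| Eligible IDE subjects consenting | Gap events lost | Gap (months) | Naive estimate | Naive false pass | Delayed-entry estimate | Delayed-entry false pass |
|---|---|---|---|---|---|---|
| All | All | 4 | 85.1% | 5% | 84.9% | 4% |
| All | All | 13 | 85.6% | 10% | 85.0% | 4% |
| All | All | 22 | 85.9% | 19% | 85.0% | 4% |
| All | Half | 13 | 85.3% | 6% | 85.0% | 4% |
| All | Half | 22 | 85.4% | 9% | 85.0% | 4.5% |
| 40% | All | 4 | 85.1% | 4.5% | 85.0% | 4% |
| 40% | All | 13 | 85.2% | 5% | 85.0% | 3.5% |
| 40% | All | 22 | 85.4% | 8% | 85.0% | 4% |

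With no gap the two analyses coincide at 85.0%, with 3% to 5% false passes. Monte Carlo error near a 4% false-pass rate is sqrt(0.04 × 0.96/1500) = 0.5 points. A separate simulation (IDE exit at 18 months, 8% attrition per year, 150 to 250 roll-overs, all gap events lost) gave +0.1 to +0.3 points and 5% to 8% false passes for a 6-month gap, against 3% to 5% with delayed entry.

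**All-cause survival.** The same formula applies with L = 1. At assumed mortality of 3% to 5% per year, the bias is +0.05 to +1.3 points across w and gaps of 4 to 22 months.

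**Shock effectiveness.** This is a proportion of episodes with no time base. If a share s of episodes falls in the gap and a fraction f of failed conversions there keeps the subject out, a true 94% becomes 0.94/(1 - 0.06 × s × f). Assuming 120 to 330 roll-overs and 3.9 person-years per subject, s runs from 120 × (4/12)/(1616 × 3.9) = 0.6% to 330 × (22/12)/(1616 × 3.9) = 9.6%. With f from 0.25 to 1, the bias is +0.01 to +0.55 points.

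**The case against.** The strongest reply is that the gap is nowhere stated. No section says that IDE subjects left that study before PAS consent. Read literally, the section 10 sentence censors anyone who had already left the IDE at that date, which leaves no gap time to credit. That reading sits badly with following consenters to 60 months if any of them had left earlier, but it makes the text ambiguous rather than shown to be biased. The example in 7.2.9 also suggests a fairly close hand-over. It is only an example of visit timing, yet it is the best timing evidence there is. This part of the reply stands, and the point has to be conditional.

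A reader might infer that the gap is guaranteed event-free. The documents do not support that. A revision or replacement (7.3) leaves the subject implanted and able to consent, and 7.2.9 would collect the event unless 11.3 excludes it. That explanted subjects cannot enroll is an inference from 9.1, since the inclusion criterion says only previously implanted. Deaths unrelated to the device are censored for Type I and do not by themselves bias it.

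A reader might also infer material inflation of shock effectiveness. That would need nearly every failed conversion in the gap to prevent consent, but an unconverted episode need not be fatal.

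The PAS has US sites only, while the IDE also ran in three other countries, so roll-over is probably well below 330. Finally, the sensitivity-analysis text (10.7.8) is largely redacted, and section 10.10 and Appendix D show no text. A rule on IDE entry could stand there.

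**Conclusion.** The point holds conditionally. The mechanism and its direction follow from sections 9.1, 10 and 10.7.1 as readable: any interval between IDE exit and PAS consent that is counted as time at risk pushes the Type I and electrode-related complication-free rates and all-cause survival upward. It does not follow that the study's results are inflated, because neither a gap nor its length is documented.

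For the primary endpoint the effect is modest at the gap that the plan's own example suggests. The upper figures need a gap near two years, nearly all eligible IDE subjects consenting, and every gap event lost, at a true rate exactly on the goal. The survival effect bears on a descriptive analysis with no performance goal. The shock-effectiveness effect is small and arises only if gap episodes are counted.

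The conflict between 11.3 and 7.2.9 over a consenter's own gap events is in the text and needs settling wherever a gap exists. Overall this is a worthwhile, inexpensive improvement, held with medium confidence.

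**What to change.** 1. **Sections 10 and 10.7.1.** Clarify that the censoring rule for subjects who had left the IDE covers roll-over subjects' own exit dates. Then analyse roll-over subjects start-stop: at risk from implant to IDE exit, out of the risk set during any gap, and re-entered at the PAS consent date at attained time since implant. Apply this to both safety endpoints and to all-cause mortality.
2. **Sections 11.3 and 7.2.9.** Reconcile the Type IV rule with the collection of earlier unreported events, so that gap events and gap time are treated alike.
3. **Sections 10.3 and 10.4.** List spontaneous episodes dated in the gap separately, and report shock effectiveness with and without them.
4. **Reporting.** Give the number of roll-over subjects and the distribution of the time from IDE exit to PAS consent.

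The cost is SAP wording and a start-stop data set built from dates the sponsor should already hold. If there is no gap, the results do not change. If there is one, a little person-time leaves the safety analyses.

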4. DEVICE DESCRIPTION

The S-ICD System is an implantable defibrillator that treats ventricular tachyarrhythmias using a subcutaneous pulse generator and a subcutaneous electrode rather than a transvenous lead. The S-ICD System received CE mark in 2009, PMA Approval in 2012 (anticipated) and is approved for distribution in the countries in which the study will be conducted. Current and future models of each device will be included in the study.

The S-ICD System consists of four devices:

- SQ-RX subcutaneous implantable defibrillator pulse generator; Model 1010 and future models.
- Q-TRAK subcutaneous electrode; Model █ and future models
- Q-GUIDE electrode insertion tool (EIT); Model █ and future models
- Q-TECH programmer; model █ and future models.

⁸ Bardy GH, Smith WM, Hood MA, et al. An entirely subcutaneous implantable cardioverter-defibrillator. *N Engl J Med.* 2010;363(1):36-44.

The S-ICD System is designed to work with the following accessories:

- Programmer telemetry wand;
- Magnet;
- Suture sleeve, included in the electrode package;
- Torque wrench, included in the pulse generator package;
- SD memory card.

The S-ICD system also requires the use of a surface ECG based “screening tool” which is used to determine the adequacy of sensing.

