5. OBJECTIVES

The primary objective of the S-ICD Post Approval Study is to document long-term safety and effectiveness outcomes associated with the implantation of the SQ-RX pulse generator and Q-TRAK electrode in commercial clinical subjects. Additional objectives include characterization of long term safety and effectiveness in subjects of varied body habitus and in traditionally underrepresented subject populations, such as women and African Americans.

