7.2.7 Pre-Discharge: Initial Device Set-Up and Programming

All device programming is at the discretion of the investigator. Investigators are encouraged to use two zones when appropriate, based on results from the S-ICD Clinical Investigation showing that dual zone programming significantly reduces adverse events for inappropriate shocks. In that study, dual zone programming was associated with a 70% relative reduction in the incidence of inappropriate shocks due to SVT and a 56% relative reduction in the incidence of inappropriate shocks due to oversensing, when compared to single zone programming.

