10.7.7 Poolability Analysis

Poolability analysis for both primary safety and effectiveness endpoint will be analyzed.

The log-rank test will be utilized to determine any relevant difference in Kaplan-Meier curves with the primary safety endpoint. A chi-square test will be used to analyze the difference in overall shock effectiveness rate for the primary effectiveness endpoint.

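### Does leaving the separate IDE and de novo analyses optional let a pooled pass stand in for the commercial implants?

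*Combined protocol and SAP*

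**What the plan says.** Section 5 states the objective as long-term outcomes with the "pulse generator and Q-TRAK electrode in commercial clinical subjects". Sections 1 and 7 define the study cohort as former IDE participants plus new implants.

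Section 10 sets the analysis population. IDE subjects "who underwent an implant attempt will contribute to the analyses of the safety and effectiveness endpoints and additional analyses". Those who do not consent to this study, or who left the IDE study earlier, "will be censored at the time of IDE study exit in the endpoint analyses" and do not count toward the enrollment target. All de novo subjects with an implant procedure are included. On splitting the cohorts, the visible text says only that "All analyses may be done separately on IDE study subjects vs de novo implants".

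Section 10.7.7 is mandatory in tone: "Poolability analysis for both primary safety and effectiveness endpoint will be analyzed". It specifies a log-rank test for safety and a chi-square test for effectiveness. The visible text names no grouping, significance level or consequence.

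Section 8.5 describes comparison with "performance goals that were derived from the same endpoints observed at shorter time periods (e.g., 1 year) in the S-ICD Clinical Investigation".

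**The concern.** The objective names commercial subjects, yet the four goal-tested endpoints are assessed in a cohort that includes premarket IDE subjects. The two groups need not behave alike. The IDE study ran in four countries (Section 3), whereas this study uses US centers. Section 4 says "Current and future models of each device will be included in the study", so de novo subjects may receive later devices. Section 7.2.7 encourages two-zone programming on the ground that "dual zone programming significantly reduces adverse events for inappropriate shocks". IDE data also informed the goals and then count toward meeting them.

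If IDE subjects do better at 60 months, a pooled pass can occur while de novo implants alone do not exceed 85%. If they do worse, pooling can hide a de novo pass. With *may* in place of *will*, the choice to show the de novo result could in principle be made after the data are seen.

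**Working it through.** **The plan's own figure.** The target of 1,616 cannot be reproduced, because the expected rates, power and attrition are redacted or not shown. The plan gives no number on the IDE versus de novo question itself.

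**Inputs from the documents.** IDE study size 330 (Section 3); target enrollment 1,616 (Section 7.1); safety goal 85.0%, tested with a one-sided 95% lower Kaplan-Meier bound using the Peto standard error (Section 10.1.2).

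**Inputs assumed.** Number of IDE subjects consenting (300, 200 or 100); the others censored uniformly at 180 to 720 days; 40% attrition by 1,800 days; 180-day rates 99% (IDE) and 98.5% (de novo); IDE 60-month rate 88%, 90% or 92%; de novo 60-month rate exactly 85%.

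**Step 1: IDE share.** If all 330 consent and count toward the target, 330/1,616 = 20.4%. If none consents, 330/(1,616 + 330) = 330/1,946 = 17.0% of the analysis set, all censored at IDE exit. What matters at 60 months is the share still at risk. With 40% attrition and both cohorts at 85%, about 824 are at risk, of whom 671 are de novo when 300 IDE subjects are followed: (824 − 671)/824 = 19%. With 100 consenting, (824 − 773)/824 = 6%.

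**Step 2: estimate needed to pass.** Solve S − 1.645 × S × √((1 − S)/n) = 0.85, with n = N × (1 − attrition) × 0.85.

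| Attrition | Pooled, N = 1,616 | De novo only, N = 1,316 |
|---|---|---|
| None | n = 1,374, S = 86.4% | n = 1,119, S = 86.6% |
| 40% | n = 824, S = 86.8% | n = 671, S = 87.0% |

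The two thresholds differ by about 0.2 points. A de novo-only bound is therefore nearly as precise as the pooled one and can be computed from data already collected.

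**Step 3: how often the pooled test passes with de novo truth at 85%** (6,000 simulated studies per cell; entries are for IDE rates of 88% / 90% / 92%).

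| IDE subjects | Pooled passes | Pooled passes, de novo bound fails | Pooled passes, log-rank (0.05) does not flag |
|---|---|---|---|
| 300 followed | 11 / 20 / 31% | 7 / 16 / 28% | 9 / 10 / 6% |
| 200 followed, 130 censored early | 8 / 14 / 21% | 5 / 10 / 17% | 7 / 8 / 7% |
| 100 followed, 230 censored early | 6 / 9 / 12% | 3 / 5 / 8% | 6 / 6 / 6% |

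The de novo-only test passes in 3% to 5%. As a plausibility check on the largest cell, the pooled true rate is about 0.85 + 0.19 × 0.07 = 86.3%. That is above 85%, so rejecting the pooled null is correct there. These are not Type I errors of the stated test.

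**Step 4: other directions.** With no 60-month difference, the pooled test passes in 3.5% to 4.2%, so there is no inflation. With de novo at 87% and IDE at 82%, pooling lowers the pass rate from 51% to 23% (300 IDE) or from 57% to 44% (100 IDE).

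**Step 5: what an obligatory split would change.** The pooled test would stay primary and the de novo result would be supportive, outside the hierarchy. Every figure in the *Pooled passes* column would be the same. Only what is displayed beside the pooled result would differ.

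**The case for a change.** The best argument for a change is that it costs almost nothing: one word in Section 10, a named grouping in Section 10.7.7, and one extra run per endpoint. Section 10.7.4 shows that the authors can write such a rule in full. For induced versus spontaneous episodes it gives the groups, the 0.05 level and the consequence. A non-significant log-rank test does not prove the cohorts alike, and the poolability text covers only the two primary endpoints.

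Part of this stands. The wording is permissive, and no visible text obliges a de novo-only estimate, least of all for the secondary endpoints. Three things limit its weight.

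- **The split is already foreseen and a comparison is required.** In a plan that combines two cohorts, IDE versus de novo is the natural poolability grouping, although the text does not say so. A log-rank comparison on that grouping produces the de novo Kaplan-Meier curve as a matter of course. With 300 IDE subjects it would flag about 50% of studies at an IDE rate of 90% and 83% at 92%.
- **The silence may not be real.** Section 10.7.8 is mostly blacked out and the body of Section 10.7.9 wholly so. Section 10.10 and Appendix D (cohort definitions) show headings only. Table 11, the subgroup matrix, is listed in the contents but does not appear. A required split or a named grouping would normally sit there.
- **The larger rates need favourable assumptions.** They set the de novo truth exactly at the goal and assume near-complete consent from an IDE cohort recruited partly outside the US. No visible text says that IDE subjects do better at 60 months.

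**Conclusion.** No change follows. This is a gap that analysts fill sensibly. The mixed cohort is declared openly, the pooled test is valid for it, and following the plan as written gives no wrong result. Cohort membership is known for every subject because the point of enrollment differs by IDE participation (Section 9.1), so the de novo estimate and bound are available whenever a reader or the FDA wants them.

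The simulated pass rates of 6% to 31% describe what pooling can do under assumed cohort differences. They do not measure a gain from rewording, since the rewording leaves each of them as it is. They rest on assumed IDE 60-month rates, consent numbers and attrition, and apply to primary safety only. The effectiveness endpoints were not computed because no episode counts are visible. Anyone reading a pooled pass should keep in mind that it speaks for the combined cohort, and look to the poolability results before applying it to commercial implants alone.
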